7.5.2 Part 2, M8891 with Cabozantinib, mRCC

Sampling time schedules for determination of M8891 and cabozantinib can be found in the SoAs (Table 4 for Part 2A and Table 5 for Part 2B).

For the PK analysis, the plasma level of M8891 and cabozantinib will be analyzed by the analytical laboratory selected under responsibility of the Sponsor, using an appropriate validated bioanalytical method. Full details of the bioanalytical method used will be described in the Laboratory Manual.

At each time point, 3 mL (2 aliquots of 1.5 mL) blood will be collected. The exact blood volume will be indicated in the Laboratory Manual.

Actual date and time of M8891 and cabozantinib administration and PK actual sampling date and time need be recorded in the eCRF.

The following M8891 and cabozantinib PK parameters in Part 2A, if applicable:

- C_{max} : Observed maximum plasma concentration
- t_{max} : Time to reach maximum observed plasma concentration
- AUC_{0-t} : Area under the concentration-time curve from time zero to the last sampling time at which the concentration is at or above the lower limit of quantification (LLOQ)
- $AUC_{0-t}/Dose$: Dose normalized AUC_{0-t} (Part 2A, M8891 only)
- $C_{max}/Dose$: Dose-normalized C_{max} (Part 2A, M8891 only)

For Part 2B the plasma concentration time profile of M8891 and cabozantinib will be described via modeling and simulation. Full details of the relevant population PK modeling work (including objectives, relevant endpoints, methodology, software etc.) will be defined in a separate pharmacology analysis plan or the study Integrated Analysis Plan. The actual elapsed time from dose will be used in the final PK modeling and parameter calculations. The results of these analyses will be described in a separate report from the CSR.

CCI

Integrated analyses across studies, such as the population PK and population PK analyses will be presented separately from the main clinical study report.

The PK concentration will be summarized by descriptive statistics per time point.

Additional analyses may be conducted on the plasma samples to further investigate the presence and/or identity of drug metabolites. Any results from such analyses may be reported separately from the clinical trial report.

At each time point, 3 mL (2 aliquots of 1.5 mL) blood will be collected. The exact blood volume will be indicated in the Laboratory Manual. For all clinical and research studies, the total blood volume (mL) drawn in a 30-day period will never exceed the 280 mL.

Details on sample shipment and handling will be provided in the Laboratory Manual.

CCI

CCI

CCI

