- Occurrence of TEAEs (including TEAEs leading to death or discontinuation of treatment) in subjects with mRCC receiving M8891 combined with cabozantinib. Any AEs that occur

or worsen between start of study intervention and 30 days after end of study intervention will be considered TEAEs

- Study clinically relevant abnormal changes in clinical laboratory measures from baseline, vital signs, ECOG performance status, and ECGs from start of study intervention to 30 days after end of study intervention
- Objective Response according to RECIST v1.1 as assessed by Investigators

Secondary endpoints:

- Duration of Response (DoR) according to RECIST v1.1 criteria as assessed by Investigators
- PFS time according to RECIST v1.1 criteria as assessed by Investigators

Part 2B, Expansion Cohort

Primary endpoints:

- Occurrence of study serious AEs including deaths from first dose of study intervention to 30 days after end of study intervention
- Study clinically relevant abnormal changes in clinical laboratory measures from baseline, vital signs, ECOG PS, and ECGs from start of study intervention to 30 days after end of study intervention
- Occurrence of TEAEs (including deaths) from start of the study intervention to 30 days after end of the study intervention
- Objective response according to RECIST v1.1 criteria as assessed by Investigators

Secondary endpoints:

- DoR according to RECIST v1.1 criteria as assessed by Investigators
- PFS time according to RECIST v1.1 criteria as assessed by Investigators

Pharmacokinetics

Part 1, M8891 Single Agent, Solid Tumors

- PK parameters of M8891 after QD dosing, as applicable: C_{max} , t_{max} , AUC_{0-t} , $AUC_{0-\infty}$, $AUC_{0-\tau}$, $t_{1/2}$, λ_z , CL/F , CL_{ss}/F , V_z/F , $Racc(AUC_{\tau})$ and $Racc(C_{max})$

Part 2, M8891 Combined with Cabozantinib, mRCC

Part 2A, Dose Escalation

- PK parameters of M8891 in terms of C_{max} , t_{max} , AUC_{0-t} on Day 1 Cycle 1, (combined with cabozantinib, single dose)
- PK parameters of M8891 in terms of C_{max} , t_{max} , AUC_{0-t} on Day 8 and Day 15 Cycle 1, and Day 1 Cycle 2 (combined with cabozantinib, multiple dose)

- PK parameters of M8891 in terms of C_{max} , AUC_{0-t} , t_{max} , t_{lag} , $t_{1/2}$, $AUC_{0-\infty}$, CL/F , V_z/F on Day -1 Cycle 1 (M8891, single dose). **CCI**
- PK parameters of cabozantinib in terms of C_{max} , t_{max} , AUC_{0-t} on Day 1 Cycle 1 (combined with M8891, single dose)

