- e. Physical exam, hematology, biochemistry, and coagulation do not have to be repeated on Day 1 if performed within 48 hours as a screening/baseline assessment.
- f. Heart rate, diastolic and systolic blood pressure, respiratory rate, body temperature.
- g. 12-lead triplicate digital ECG will be performed with 2-minute intervals after at least 10 minutes rest in supine position. On Cycle 1 Day 1 and Day 15 at pre-dose and 1, 2, 4, 5, 6, 8, 12 hours and 24 hours post-dose (\pm 15 minutes) and on pre-dose on Day 8. The SMC may decide that the Day 15/Day 16 assessment can be waived in case no relevant drug accumulation is being observed. ECG assessments at subsequent cycles will be performed pre-dose at time points as indicated in the table. ECGs should be performed directly before PK sampling time points on days where both assessments are performed.
- h. Hemoglobin, white blood cell count, differential, platelet count, creatinine, creatinine clearance AST, ALT, GGT, AP, lipase, amylase, BUN, total bilirubin, total protein, albumin, uric acid, sodium, chloride, bicarbonate, potassium, calcium, phosphorus, magnesium and glucose, PT, aPTT and INR.
- i. Standard urine test, and pregnancy test will be done at each visit after Cycle 2 (corresponds to women of childbearing potential).

CCI

CCI

CCI

- m. PK time points: 3 mL (2 aliquots of 1.5 mL) blood each at following time points: QD dosing: Cycle 1 Day 1: 0 hour (pre-dose within 60 minutes prior to each treatment administration) and 1 (\pm 10 minutes), 2 (\pm 10 minutes), 3 (\pm 10 minutes), 4 (\pm 20 minutes), 5 (\pm 20 minutes), 6 (\pm 30 minutes), 8 (\pm 30 minutes), 12 hours post-dose (\pm 60 minutes), on Day 2 at 24 hours post-dose (before next drug administration) (\pm 60 minutes). Cycle 1 Day 8: 0 hour (pre-dose within 60 minutes prior to treatment administration), Cycle 1 Day 15: 0 hour (pre-dose within 60 minutes prior to each treatment administration) and 1 (\pm 10 minutes), 2 (\pm 10 minutes), 3 (\pm 10 minutes), 4 (\pm 20 minutes), 5 (\pm 20 minutes), 6 (\pm 30 minutes), 8 (\pm 30 minutes), 12 hours post-dose (\pm 120 minutes), on Day 16 at 24 hours post-dose (before next drug administration) (\pm 60 minutes), 63 mL blood in Cycle 1. Cycle \geq 2 Day 1: 0 hour (pre-dose within 60 minutes prior to each treatment administration).

CCI

CCI

- p. Pre-dose; optional blood sample: collection will only be performed after an Informed Consent Form has been signed.

CCI

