- Imaging analysis must be using the same technique during the study, e.g. it's not allowed to use CT scan at baseline then change to MRI during the study. Tumor response will be assessed, within 1 week prior to Day 1 of Cycles 3, 5, and 7, and every third cycle thereafter. Subjects who discontinue treatment will undergo EOT visit procedures.

Table 4

Schedule of Pharmacokinetic, Electrocardiogram Assessments and Food Guidance during Part 2A M8891 Combined with Cabozantinib, mRCC, Dose Escalation

Treatment Day	Time h (\pm min) ^{a,b}	ECG ^c	PK M8891	PK Cabozantinib
Day -1, C1	Pre-dose (-60 min)	X	X ^d	
	1 (\pm 5)		X ^d	
	2 (\pm 10)	X	X ^d	
	3 (\pm 15)		X ^d	
	4 (\pm 15)		X ^d	
	6 (\pm 15)	X	X ^d	
	8 (\pm 15)		X ^d	
D1 C1	Pre-dose (-60 min)	X	X	X
	1 (\pm 5)		X	
	2 (\pm 10)	X	X	X
	3 (\pm 15)		X	
	4 (\pm 15)		X	
	6 (\pm 15)	X	X	X
D8 C1	Pre-dose (-60 min)	X	X	X
	2 (\pm 5)	X	X	X
D15 C1	Pre-dose (-60 min)	X	X	X
	1 (\pm 5)		X	
	2 (\pm 10)	X	X	X
	3 (\pm 15)		X	
	4 (\pm 15)		X	
	6 (\pm 15)	X	X	X
D1C2	Pre-dose (-60 min)	X	X	X
	2 (\pm 10)	X	X	X
D1C3-5	Pre-dose (-60 min)	X		
	1 (\pm 5)	X		
D1C7 (and Day 1 of every third cycle)	Pre-dose (-60 min)	X		
	1 (\pm 5)	X		

C: Cycle; D: Day; ECG: Electrocardiogram; eCRF: Electronic case report form; mRCC: Metastatic renal cell carcinoma; PK: Pharmacokinetics.

a. At visits where assessment time points (ECG and PK) coincide with each other

- 1) Perform vital signs assessments at first
- 2) ECG assessments slightly before the specific collection time point
- 3) PK assessments at scheduled collection time point.

b. Actual collection times should be documented in the eCRF.

- c. Standard triplicate (within 2 min) 12-lead ECG will be obtained after the subject has been rested in semi-recumbent position for at least 5 min at the indicated times. ECGs will be also performed during the End of Treatment and Safety Follow-up Visit (30 ± 7 days). Triplicate ECGs will be read locally. The calculated QTcF interval average of the three 12-lead ECGs must be ≤ 450 ms for males and ≤ 470 ms for females for eligibility. Subjects, in which the calculated QTcF interval average increases to > 500 ms or > 60 ms change over baseline during treatment, must interrupt study treatment until further clinical evaluations (See Section 7.4.5).

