Each part of the study will include a Screening period of up to 28 days, a study intervention period consisting of 21-day cycles of M8891 single agent (Part 1) and M8891 combined with cabozantinib (Part 2), an End of Study Intervention visit (within 7 days), and a Safety Follow-up period of 30 (\pm 7) days. Subjects who discontinue study intervention for any reason will complete the End of Study Intervention and Safety Follow-up visits. In Part 2A, before Cycle 1 of all dose levels, subjects will receive a single dose of M8891 in the morning in fed conditions (Day -1, Cycle 1) and the PK profile of M8891 will be evaluated pre-dose, 1, 2, 3, 4, 6, 8 and 24h (Day 1, Cycle 1) after administration (Section 5.1.3.2.1). Subsequently on Day 1 Cycle 1, subjects will initiate

treatment with M8891 combined with cabozantinib QD orally every morning under fasted conditions.

Study duration per subject is approximately 8 months for Part 1, and 12 months for Part 2 including screening, treatment and follow up.

[figure not shown]
The design of this study is presented in

Figure 1 and a detailed Schedule of Assessments (SoAs) is provided in Table 1, Table 2, Table 3, Table 4, and Table 5.

Figure 1

Study Design

AE: Adverse event; DL: Dose level; FBE Free-base equivalent; MTD: Maximum tolerated dose; QD: Once daily; SMC: Safety Monitoring Committee; RP2D: Recommended Phase 2 Dose; mRCC: metastatic renal cell carcinoma; **CCI** [REDACTED].

- a. The MTD of M8891 single agent will be defined, and RP2D of M8891 single agent suggested, by the SMC.
- b. Subjects should have progressed to 1 or more previous lines of systemic anticancer therapy, excluding treatment with cabozantinib.
- c. Cabozantinib will be given at the approved 60 mg FBE daily dosage with dosage adjustments to 40 mg or 20 mg permitted to manage AEs.

CCI [REDACTED]

CCI [REDACTED]

- f. 30 subjects evaluable for response.
- g. The DLT assessment period for Part 2A is the Cycle 1 (= 22 days, 21 days of M8891 combined with cabozantinib, preceded by 1 day of M8891 alone) of study treatment. The rest of the Cycles in Part 2A are 21-day cycles of M8891 combined with cabozantinib.
- h. See Section 8.5.1 for the Bayesian two-parameter logistic regression model.

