5.1.3.2 Part 2, M8891 combined with Cabozantinib, mRCC

5.1.3.2.1 Part 2A, Dose Escalation

In Part 2A, before Cycle 1 Day 1 of all dose levels, subjects will receive a single dose of M8891 in the morning in fed conditions (Day -1, Cycle 1) and the PK profile of M8891 will be evaluated. Subsequently on Day 1 Cycle 1, subjects will initiate treatment with M8891 combined with cabozantinib QD orally every morning under fasted conditions. Following Cycle 1, all other cycles will start with Day 1 and will include only the 21 days of M8891 combined with cabozantinib.

Subjects will accrue in cohorts of 3 subjects for evaluation of M8891 combined with cabozantinib 60 mg QD (with dosage adjustments to 40 or 20 mg FBE permitted to manage AEs as described in Section 6.5.5). Both drugs will be taken in the morning in fasted conditions. A Bayesian 2-parameter logistic regression model with overdose control will be used to assist the SMC with dose selection for the next cohort and to determine the MTD/RDE of M8891 combined with cabozantinib 60 mg QD for Part 2B.

Three pre-specified dose levels of M8891 are planned (20 mg, 35 mg and 60 mg) combined with 60 mg of cabozantinib. Dose levels may be added or skipped for others that are not part of the pre-specified set but they will never exceed the dose level of M8891 that has already been declared to be safe in Part 1. The dose levels have been chosen based on preliminary data from the ongoing Part 1 of the study. At the time of Amendment 2, M8891 single agent was being investigated at 60 mg QD in subjects with solid tumors. PK^{CC} studies have shown that the 20, 35 and 60 mg QD regimens reached pre-selected exposure (≥ 1500 ng/mL) at steady state while CCI

. Three and 5 Grade ≥ 3 TEAEs have been seen at 20 and 35 mg QD regimen, respectively. One DLT (Grade 4 thrombocytopenia) has been observed in the ongoing 60 mg QD cohort (Refer to the M8891 IB).

Dose escalation of the combination will proceed until the RDE of M8891 is reached in combination with a fixed dose of cabozantinib or dose escalation ends due to occurrence of an MTD, or the SMC decides ending dose escalation following review of safety, tolerability, and PK results, whatever occurs first. The maximum dose of M8891 combined with cabozantinib will not exceed the MTD of M8891 in monotherapy determined in Part 1 of the study.

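### In Part 2A, AUC0-t covers 6 h (or 2 h) of the 24 h dosing interval on the multiple-dose days, so it measures only part of steady-state exposure and does not match the 24 h areas on Day -1 and in Part 1

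*Protocol*

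**What the plan says.** Protocol 7.5.2 lists the Part 2A parameters for M8891 and cabozantinib: Cmax, tmax and AUC0-t, plus dose-normalised Cmax and AUC0-t for M8891. AUC0-t is the "Area under the concentration-time curve from time zero to the last sampling time" at which the concentration is quantifiable. The list for Part 1 (7.5.1) also has an AUC over the dosing interval (AUCtau); the visible Part 2A list does not.

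The synopsis and Table 6 apply Cmax, tmax and AUC0-t for M8891 "on Day 8 and Day 15 Cycle 1, and Day 1 Cycle 2 (combined with cabozantinib, multiple dose"). The synopsis does the same for cabozantinib. Dosing is daily: "treatment with M8891 combined with cabozantinib QD orally every morning under fasted conditions" (5.1.3.2.1).

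The sampling times differ by day and Part:
- Part 2A Day -1 (5.1): "the PK profile of M8891 will be evaluated pre-dose, 1, 2, 3, 4, 6, 8 and 24h (Day 1, Cycle 1) after administration".
- Part 2A from Day 1 on (Table 4): the last M8891 sample is at 6 h on Day 1 and Day 15, and at 2 h on Day 8 and Cycle 2 Day 1.
- Part 1 (Table 1, footnote m): the Day 1 profile ends "on Day 2 at 24 hours post-dose (before next drug administration"), and the Day 15 profile "on Day 16 at 24 hours post-dose (before next drug administration").

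Protocol 8.5.4.2 assesses dose proportionality on AUC over the dosing interval (or to infinity) and Cmax for Day 1 and Day 15, without limiting this to Part 1. Table 13 asks for at least three valid post-dose concentrations to obtain any PK parameter.

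**The concern.** One parameter name stands for three different quantities: an area over 24 h, over 6 h or over 2 h. Dividing by dose does not remove the difference.

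The Part 2A secondary objective is M8891 exposure after single and multiple dosing with cabozantinib. The visible area endpoint for the multiple-dose half of it observes a quarter of the interval at best. An area over the first 6 h depends heavily on absorption. It can understate a change in clearance, which is one way a drug interaction would show itself. Section 3.3.3 relies on monitoring cabozantinib exposure and estimates at most a 1.2-fold rise, and that area also stops at 6 h.

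PK is among the data the Safety Monitoring Committee reviews in Part 2A, and escalation may end on safety and/or PK (5.1.3.4).

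**Working it through.** The plan states no figure to reproduce. As a check that the Part 1 schedule is read correctly: 10 samples (Day 1 to 2) + 1 (Day 8) + 10 (Day 15 to 16) = 21, and 21 x 3 mL = 63 mL, which matches Table 1 footnote m.

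**Windows (no assumptions needed), M8891**

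| Profile | Last sample | Missed of 24 h | Post-dose samples |
|---|---|---|---|
| Part 1 Day 1, Day 15 | 24 h | 0 | 9 |
| Part 2A Day -1 | 24 h | 0 | 7 |
| Part 2A Day 1, Day 15 | 6 h | 24 - 6 = 18 | 5 |
| Part 2A Day 8, Cycle 2 Day 1 | 2 h | 24 - 2 = 22 | 1 |

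The 24 h point for Day -1 is the Day 1 pre-dose draw. Cabozantinib has post-dose samples at 2 and 6 h on Day 1 and Day 15, and at 2 h only on Day 8 and Cycle 2 Day 1. So M8891 on Day 8 and Cycle 2 Day 1 (one point), and cabozantinib on every day (two points or one), fall below the three-point minimum in Table 13.

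**Size (assumed PK).** The documents give no half-life or absorption rate. I used a one-compartment oral model with unit dose every 24 h:

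C(t) = sum over i = 0 to n-1 of ka/(ka-ke) x [exp(-ke(t+24i)) - exp(-ka(t+24i))], with ke = ln 2 / half-life.

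The grid is ka 0.5, 1.0, 1.5 /h, half-life 4, 6, 8, 12, 18, 24 h, and n = 15 doses.

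1. *Window effect.* AUC0-6/AUC0-24 runs from 0.28 (ka 0.5, half-life 24 h) to 0.61 (ka 1.5, half-life 4 h). With identical exposure, the 6 h area therefore reads 1 - 0.61 = 39% to 1 - 0.28 = 72% below the 24 h area. On a wider grid (ka 0.5-2 /h, half-life 3-48 h), using the protocol's sampling times, the ratio is 0.26-0.71. For the 2 h area it is 0.08-0.17.
2. *Sensitivity to clearance.* If clearance falls 30%, AUC over the interval rises by 1/0.7 = 1.43. AUC0-6 rises by 1.18 (half-life 4 h) to 1.38 (24 h). For a true 1.2-fold rise, AUC0-6 shows 1.09 to 1.18.
3. *Recovering the full interval.* Take Day 15 samples at pre-dose, 1, 2, 3, 4 and 6 h, set the 24 h value equal to the pre-dose value, and use the linear-up/log-down rule. The result is within 4% of the true AUC over the interval. With the cabozantinib times (pre-dose, 2, 6 h) it is within 9%, on the same assumed range.
4. *Carry-over on Part 2A Day 1.* This day is labelled single dose but follows the Day -1 dose by 24 h. AUC0-6 with n = 2 over AUC0-6 with n = 1 is 1.02 to 1.76.
5. *The planned food comparison.* Day -1 against Part 1 Day 1, each on its own sampling times, gives 0.99-1.00 on the wider grid. The window does not distort it.

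**The case against.** A reader might infer that the plan will report a large false fall in M8891 exposure with cabozantinib. The documents do not support that. The one visible comparison of Part 2A with Part 1 is Day -1 fed against Part 1 fasted (Table 4, note d), and both profiles reach 24 h. Dose levels compared on the same day share a window. The 39-72% is what a 6 h versus 24 h comparison would show if someone made it.

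The link to dose selection is also loose. The exposure criterion visible in 5.1.3.2.1 is a concentration (at least 1500 ng/mL at steady state), and no visible rule uses AUC0-t. The loss of sensitivity depends on half-life: at 24 h, AUC0-6 rises 1.35-1.38 against a true 1.43, which is a modest loss. Part 2A is small (6-15 subjects) and descriptive. All of this stands, and it limits the consequence.

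Parts of the PK text are redacted, the 7.5.2 list is qualified as applying where applicable, and details are left to the Integrated Analysis Plan. The plan supplied is version 1.0, covers monotherapy only, and is to be amended if combination parts are added. It does have a rule for an interval that ends after the last sample (16.1.2), but that rule needs a terminal slope. The slope requires at least three points excluding tmax and an observation span of at least two half-lives, failing which results are flagged. On Part 2A Day 15 the most favourable case is tmax at 1 h, leaving 2, 3, 4 and 6 h: a span of 4 h, which meets the criterion only for a half-life of 2 h or less. Carrying the rule over would not settle the point. The amended plan is, however, a proper place for the fix.

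**Conclusion.** The point holds for what AUC0-t measures. On the visible text, the Part 2A multiple-dose area covers 6 of 24 h on Day 15 and 2 of 24 h on Day 8 and Cycle 2 Day 1. AUC0-t and AUC0-t/Dose are not comparable between these days and Day -1 or Part 1. Section 8.5.4.2 calls for an interval or infinity area that 7.5.2 does not list for Part 2A. These statements rest on the schedules alone.

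The percentages rest on an assumed one-compartment model. The range was applied to cabozantinib without a source, so the 9% is illustrative. The point does not extend to the food comparison or to same-day dose comparisons, and it does not show that a dose decision would be wrong. It is worth correcting because a better measure is available from samples already scheduled.

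**What to change.** Amend 7.5.2, Table 6 and the synopsis, or put the following in the amended Integrated Analysis Plan:

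1. Add Day 15 AUC over the dosing interval for M8891, taking the pre-dose concentration as the 24 h value. State the steady-state assumption and check it against the Day 8 and Cycle 2 Day 1 troughs. Use this area for multiple-dose exposure, dose proportionality and comparison with the same parameter on Part 1 Day 15.
2. Rename the Day 1 and Day 15 area AUC0-6 and compare areas only over equal windows. A 0-6 h area can be derived for Part 1 and Day -1, since 6 h is sampled there too. Note that Part 2A Day 1 is the second M8891 dose, so it is not a single-dose reference against Part 1 Day 1, and that Day -1 is fed.
3. Drop AUC0-t on Day 8 and Cycle 2 Day 1. Report the pre-dose and 2 h concentrations.
4. For cabozantinib, reconcile with Table 13: either state an exception for a Day 15 interval AUC built the same way, or report concentrations and troughs only.

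The cost is wording and a few derived parameters, with no new samples. The downside is that the interval AUC rests on steady state, which the scheduled troughs can check.

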7.7 Other Assessments

Not applicable.

8 Statistics

Statistical methodology is generally described within this Section 8. Additional details will be provided in an Integrated Analysis Plan.

8.1 Sample Size

8.1.1 Part 1, M8891 Single Agent, Solid Tumors

A Bayesian model is applied to assist the SMC in dosing decisions. For details on the model see Section 8.5.3.1

As this is the dose escalation part of the trial, with M8891 single agent, sample size cannot be exactly prespecified, but depends among other things on the number of DLTs seen.

The sample size for Part 1 dose escalation (QD) is capped at a maximum of 42 subjects.

At least 6 subjects need to have been treated at the suggested MTD or RP2D. That might necessitate the enrollment of additional subjects after dose escalation was stopped. For this sample size assessment, it is assumed that it is not necessary to enroll additional subjects to fulfill this criterion.

It is anticipated that 36 evaluable subjects (8 dose levels with 3 to 12 subjects, e.g. assuming a scenario with 5 dose levels with 3 subjects, 2 dose levels with 6 subjects (2 cohorts) and one dose level with 9 subjects (3 cohorts) may be needed in order to determine the MTD of QD dosing of M8891.

The anticipated total number of evaluable subjects is approximately 36 (42 if the maximal sample size stopping criterion is reached).

